## 6. GENERAL STATISTICAL CONSIDERATIONS

### 6.1. General Principles

All continuous variables will be summarized using the following descriptive statistics: n (non-missing sample size), mean, standard deviation (SD), median, quartiles, maximum, and minimum. The frequency and percentages (based on the non-missing sample size) of observed levels will be reported for all categorical measures. In general, all data will be listed, sorted by treatment and subject, and when appropriate by visit number within subject.

All safety summary tables and figures will be summarized by the following treatment groups in the following order:

- $4 \times 10^7$  PFU dose
- $4 \times 10^8$  PFU dose
- $4 \times 10^9$  PFU dose
- Placebo

The safety analysis in this SAP will include subjects from Stage 1, Stage 2a, and Stage 2b.

All microbiological activity and benefit to risk analyses, including the interim analysis, will be summarized by the following treatment groups in the following order:

- IV Bacteriophage Selected Dose
- Placebo

with “IV Bacteriophage Selected Dose” being replaced with the selected IV Bacteriophage dose found in the interim analysis, described in Section 8.3. The ‘IV Bacteriophage Selected Dose’ group will include subjects from Stage 2a and Stage 2b who received the selected IV bacteriophage dose. The ‘Placebo’ group will include subjects from Stage 2a and Stage 2b who received the placebo.

### 6.2. Timing of Analyses

There will be one planned interim analysis of the primary endpoints after all randomized subjects for Stage 2a have completed follow-up through Day  $30 \pm 7$  or the last study visit for those who withdrew early. Enrollment will be held until the dose for Stage 2b is determined from the planned interim analysis. More details regarding the interim analysis can be found in Section 6.6.

The Data and Safety Monitoring Board (DSMB) will evaluate safety at pre-specified intervals; however, ongoing review and summary of subjects’ safety will occur to allow for early detection of a safety signal that may result from an AE. The DSMB will advise the trial sponsor on whether to continue, modify, or terminate the trial based on risk assessment.

The final analysis will be performed after database lock.

## 6.3. Analysis Populations

The primary analysis will be performed using the ITT Population.

Reasons for exclusion from the screened analysis population are summarized in [Table 10](#), [Table 11](#), and [Table 12](#), while reasons for exclusions from the rest of the analysis populations (ITT, Safety, PK) are summarized in [Table 8](#) by treatment group. Individual subject listing of exclusion reasons is also provided in [Listing 5](#). Excluded subjects might satisfy multiple criteria justifying their exclusion but will have only one reason indicated in [Table 8](#) and [Listing 5](#). The exclusion reason indicated will be determined by first exclusion reason met based on the following rules in the order they are listed for each analysis population.

### 6.3.1. Screened Population

The screened population will consist of all subjects who undergo the Screening Visit and receive a patient identification (PID) number.

### 6.3.2. Intent-to-Treat (ITT) Population

The ITT Population will consist of all randomized subjects regardless of whether or not they receive study product or placebo. ITT analysis will be performed based on the treatment that a subject is randomized to receive.

### 6.3.3. Safety Population

The Safety Population will consist of all randomized subjects who will receive at least some amount of study product or placebo. Subjects will be analyzed based on the treatment received.

### 6.3.4. Pharmacokinetics (PK) Population

The PK Population will consist of all randomized subjects who will contribute at least two samples each of sputum and blood.

## 6.4. Covariates and Subgroups

An exploratory analysis of the primary outcomes will be conducted to explore whether estimated treatment effects vary significantly between subcategories of trial subjects. Bacteriophage susceptibility will be the only pre-specified subgroup analyzed, however exploratory analyses of the primary endpoints may be performed using any other subgroups of interest.

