10.2 Sample Size Considerations

The sample size for Stage 2 (Stage 2a/2b) was determined using the DOOR outcome measure. The sample size was calculated to provide desired precision of the estimate of the DOOR probability in order to describe the benefit to risk profile of a single dose of IV bacteriophage in clinically stable CF subjects with *P. aeruginosa* in expectorated sputum. If the true DOOR probability comparing IV bacteriophage and placebo is 70%, when the total sample size in each arm is 20 (combining subjects from Stages 2a and 2b), the two-sided normal approximate 95% confidence interval for DOOR probability is calculated at 51% and 89%, respectively, with the lower limit larger than 50% (see Section 10.5.5).

An interim analysis will be performed when the 8 subjects per arm in Stage 2a ($40\% = 8/20$) have completed their Day 8 + 3 days Follow-up Visit (Section 10.4.2). Based on the observed data, two of the doses of IV bacteriophage therapy will be dropped from the study at the interim analysis, and the planned sample size will be re-evaluated as to whether it provides the desired precision of estimates of the DOOR probability for a selected dose and placebo. If necessary, after completion of Stage 2a and per details in Section 10.4.2, the sample size will be increased up to 17 subjects for each of the two arms in Stage 2b (a total of up to 25 for the placebo arm and up to 25 for the selected bacteriophage dose in Stage 2).

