10.5 Final Analysis Plan

10.5.1 General Considerations

The SAP, which includes more technical and detailed elaboration of the principal features stated in the protocol, will be prepared separately and finalized before the interim analysis.

Safety will be assessed by estimating the occurrence of Grade 2 or higher treatment-emergent AEs in the IV bacteriophage therapies compared to placebo through Day 30 ± 7 days.

Microbiological activity will be assessed by estimating changes in $\log_{10} P. aeruginosa$ CFU/mL (total and each morphology) in sputum cultures from baseline through Day 30 ± 7 days.

The benefit to risk profile will be assessed by comparing the DOOR of IV bacteriophage arms and placebo arm through Day $8 + 3$ days. The DOOR will be analyzed by estimating the DOOR probability (Section 10.5.5), (i.e., the probability of a randomly selected subject having a better DOOR if assigned to receive an IV bacteriophage therapy compared to placebo).

All statistical calculations will be performed using up-to-date versions of SAS version 9.4 or higher (SAS Institute Inc., Cary, NC, USA) or language and environment for statistical computing 3.6.1 or higher (R Foundation for Statistical Computing, Vienna, Austria), unless otherwise specified. All PK analyses will be performed using NONMEM version 7.3 or higher (ICON Development Solutions, [name]). For continuous variables, summary statistics will include sample size, mean, SD, median, quartiles, minimum, and maximum values. Frequencies and percentages will be calculated for categorical variables. All reported confidence intervals will be two-sided 95%. Graphical displays will be produced.

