10.5.6 Subgroup and Adjusted Analyses for Primary Endpoints

As an explanatory analysis, subgroup analyses of the primary outcomes may be conducted to explore whether estimated treatment effects vary significantly between subcategories of trial subjects, including, but not limited to, bacteriophage susceptibility and presence of co-infection with other organisms recovered on sputum cultures collected during the study period. In addition, the primary endpoints will adjust for pre-randomization variables, which might reasonably be expected to be predictive of favorable outcomes.

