### 8.2.4. Subgroup Analyses

A subgroup analysis of the primary endpoints will be conducted to explore whether estimated treatment effects vary significantly between subcategories of trial subjects, including bacteriophage susceptibility and presence of co-infection with other organisms recovered on sputum cultures. Analysis of the difference in

mean change between IV bacteriophage and placebo arms and the  $\log_{10}$ -transformed difference in mean change, along with the corresponding 95% CIs, will be presented by subgroup in [Table 22](#). A forest plot of the differences in *P. aeruginosa* colony counts is presented by subgroup in [Figure 8](#) and a forest plot of differences in the  $\log_{10}$  *P. aeruginosa* colony counts is presented by subgroup in [Figure 9](#). Analysis of the primary DOOR endpoint at Day 8 will be presented by subgroup in [Table 29](#) and a contingency table of DOOR by subgroup, treatment group, and time point will be presented in [Table 30](#). A forest plot of DOOR probability in subgroups will be presented in [Figure 11](#).

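### The subgroup plan asks whether treatment effects differ between subgroups but reports only a separate interval within each, so nothing planned answers the question

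*SAP*

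**What the plan says.** The same aim appears three times. SAP 6.4 has "An exploratory analysis of the primary outcomes will be conducted to explore whether estimated treatment effects vary significantly between subcategories of trial subjects". SAP 8.2.4 has "A subgroup analysis of the primary endpoints will be conducted to explore whether estimated treatment effects vary significantly between subcategories of trial subjects". Protocol 10.5.6 says subgroup analyses may be done to "explore whether estimated treatment effects vary significantly between subcategories of trial subjects".

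The outputs named for this aim are:

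- **Table 22** (addendum on undetectable counts: Tables 7 and 8): difference between arms in mean change, with a Welch 95% CI, per subgroup and time point, on the log10 and untransformed scales.
- **Table 29** (addendum Tables 18 and 19): DOOR probability with a 95% CI per subgroup, with and without inverse probability weighting.
- **Figures 8, 9 and 11** (addendum Figures 7–10, 13 and 14): forest plots by subgroup.
- **Table 30** (addendum Tables 20 and 21): counts and percentages by DOOR rank, with no effect estimate or interval.

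Neither the SAP nor the addendum contains an interaction term, a heterogeneity test, or an estimate of the difference between subgroup effects. Footnote b of Table 29, repeated in addendum Tables 18 and 19, says superiority is concluded when the lower limit exceeds 0.5. It therefore applies to each subgroup row.

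**The concern.** Whether an effect varies between subgroups is a question about the difference between two effects. One interval that excludes the null beside another that does not is no evidence of a difference: the second may be wider, or its estimate lower by chance. The susceptible and non-susceptible strata will each hold a fraction of 20–25 subjects per arm, so such discordance is common even when nothing differs.

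The plan makes the misreading easy. SAP 8 rests conclusions about treatment effects on confidence intervals, and the Table 29 footnote can produce a superiority conclusion in one susceptibility row and not in the other. Susceptibility is the only subgroup that SAP 6.4 pre-specifies, and it is not screened before dosing. Readers will look to this table to learn whether activity depends on a susceptible isolate.

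**Working it through.** **Inputs from the documents** (Protocol 10.2 and 10.5.1). Effect: "If the true DOOR probability comparing IV bacteriophage and placebo is 70" per cent. Size: "when the total sample size in each arm is 20 (combining subjects from Stages 2a and 2b"), rising to "a total of up to 25 for the placebo arm and up to 25 for the selected bacteriophage dose in Stage 2". Intervals are two-sided 95%.

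**Assumptions, not in the documents.** Susceptible share 30%, 50% or 70%; SD of log10 change 1.0–2.0; a 1 log10 difference from placebo (the documents expect at least 1 log10 against baseline, not against placebo).

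**1. The plan's own figure.** Protocol 10.2 says: "confidence interval for DOOR probability is calculated at 51% and 89%, respectively, with the lower limit larger than 50" per cent. With the Wilcoxon–Mann–Whitney null variance, SE = √[(n₁+n₂+1)/(12·n₁·n₂)]. At 20 per arm, SE = √(41/4800) = 0.0924, and 0.70 ± 1.96 × 0.0924 = 51.9% to 88.1%, within a point of each stated limit. The stated half-width of 0.19 implies SE = 0.19/1.96 ≈ 0.097.

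**2. DOOR, same true value of 0.70 in both strata.** The chance that a stratum's lower limit exceeds 0.5 is p = 1 − Φ(1.96 − 0.20/SE). The chance that exactly one does is p_a(1 − p_b) + p_b(1 − p_a).

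| Per arm | Split | SEs | p_a, p_b | Exactly one |
|---|---|---|---|---|
| 20 | 10/10 | 0.132, 0.132 | 0.327, 0.327 | 44% |
| 20 | 14/6 | 0.111, 0.174 | 0.437, 0.210 | 46% |
| 25 | 50:50 | 0.118, 0.118 | 0.397, 0.397 | 48% |
| 25 | 70:30 | 0.099, 0.154 | 0.524, 0.254 | 51% |

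Scaling to the implied SE of 0.097 gives 42–49%. Simulation with ordinal ranks (bacteriophage 35/35/30/0%, placebo 10/25/65/0% in ranks 1–4, DOOR probability 0.70), a Halperin-type interval and 20,000 runs gives 48–55%.

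**3. log10 change, same 1 log10 effect in both strata, 20 per arm, Welch intervals.** Simulated chance that exactly one interval excludes zero, in either direction:

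| SD | 10/10 | 14/6 |
|---|---|---|
| 1.0 | 50% | 57% |
| 1.2 | 49% | 53% |
| 1.5 | 41% | 43% |
| 2.0 | 30% | 30% |

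Letting the stratum sizes vary at random gives 29–59%.

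**4. By direction.** At SD 1.2, an effect in the susceptible stratum only appears in about 24% of trials at 10/10, 43% with 14 susceptible and 6 not, and 11% with 6 susceptible and 14 not.

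**5. No effect in either stratum.** Welch intervals: about 9% (2 × 0.05 × 0.95 = 9.5% by formula). DOOR, counting only lower limits above 0.5: about 4% (2 × 0.025 × 0.975 = 4.9%).

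**6. The direct contrast under identical effects.** For log10 change with a Welch–Satterthwaite interval, it excludes zero in about 5% of trials. For DOOR with summed plug-in variances, it does so in 8–11%, so that interval is somewhat too narrow in small strata.

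**7. What the contrast can resolve.** For DOOR, the half-width is 1.96·√(SE_a² + SE_b²): ±0.37 (10/10) to ±0.40 (14/6) at 20 per arm, and ±0.33 to ±0.36 at 25. Power for a true difference of 0.20 is 16–19% at 20 per arm and 19–22% at 25.

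**The case against.** The strongest reply is that nothing formal hangs on this. SAP 6.4 labels the analysis exploratory, Protocol 10.5.6 makes it optional, the trial has no formal hypothesis tests, and susceptibility testing itself depends on sample availability (Protocol 7.2.2). No rule says that differing intervals mean differing effects. This stands: the risk is a misread exploratory table, not an inflated error rate for a primary conclusion. It does not supply the missing analysis, and the superiority footnote on each row works against the exploratory label.

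A second reply is that the contrast has so little power that it will rarely settle anything. That is true, and it is why a non-significant contrast must not be read as homogeneity. But a wide interval shows that limit openly; two separate intervals hide it.

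A reader might go further and infer that the planned display will usually show an effect in susceptible subjects and none in the others. The documents do not support that. They give neither the susceptible share nor the SD, the discordance rates count both directions, and the susceptible-only pattern ranges from about 11% to 43% at SD 1.2 and a 1 log10 effect, depending on the split. Nor is discordance common if the product has no effect.

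**Conclusion.** The concern holds: the stated question has no planned estimate. With identical true effects, separate intervals would disagree in about 42–55% of trials at the design DOOR of 0.70 with 20–25 per arm. For log10 change the figure is about 30–57% at 20 per arm, with roughly half in each direction at an even split. If there is no effect it is about 4–9%. The DOOR figures rest on the plan's own effect and sample size plus an assumed susceptible share of 30–70%; the log10 figures also rest on an assumed SD and effect. The consequence is limited to how exploratory subgroup results are read. The change is still worth making because it is cheap and answers the question that the plan sets.

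**What to change.** For each subgroup factor, add the between-subgroup contrast with a 95% CI.

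- **log10 CFU** (Table 22, addendum Tables 7 and 8): the difference between the two subgroup differences, with a Welch–Satterthwaite interval, at each time point. Name Day 30, the primary endpoint time, as the main one.
- **DOOR by Day 8** (Table 29, addendum Tables 18 and 19): the difference between the two DOOR probabilities, with an interval. Because summed plug-in variances run narrow in small strata, check it by bootstrap or permutation.
- **Footnote:** remove the superiority statement from Table 29 and addendum Tables 18 and 19.
- **Text in SAP 6.4 and 8.2.4:** effect modification is described from the contrast and not by comparing the separate intervals; power is about 16–22% for a DOOR difference of 0.20; an interval covering zero does not show homogeneity.
- **Shell correction:** the implementation notes for Table 22 and addendum Tables 7 and 8 list the susceptible category twice and omit the non-susceptible one, which the contrast needs.

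The cost is a little code and some extra rows, more for co-infection, which is one factor per organism. The intervals will be wide. No new data are needed, and the main analyses do not change.

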## 6.5. Missing Data

While all efforts will be made to minimize missing data, some missing data is expected. Whenever possible, subjects terminating from the study early will be given an early termination (ET) visit during which the available components of DOOR and related measures can be recorded. A sensitivity analysis of DOOR will be performed using inverse probability weighting (IPW) to reduce the bias in DOOR outcome caused by missing data, assuming a missing at random (MAR) model (see [Section 8.1.3.1](#)). No other endpoints will be analyzed using techniques for missing data.

The effect that any missing data might have on results will be assessed via the inclusion of the IPW sensitivity analysis.

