3.3 Study Endpoints or Outcome Measures

3.3.1 Primary

- Number of grade 2 or higher treatment-emergent AEs through Day 30 ± 7 .
- Change from baseline to Day 30 ± 7 days in \log_{10} *P. aeruginosa* total colony counts in quantitative sputum cultures after administration of IV bacteriophages/placebo.
- Desirability of Outcome Ranking (DOOR) using the greatest reduction by Day $8 + 3$ days Follow-up Visit.

More desirable	Rank 1	No SAE (related to study product) and $> 2 \log_{10}$ reduction in P. aeruginosa CFU/mL
↑	Rank 2	No SAE (related to study product) and $1-2 \log_{10}$ reduction in P. aeruginosa CFU/mL
↓	Rank 3	No SAE (related to study product) and $< 1 \log_{10}$ reduction in P. aeruginosa CFU/mL
Less desirable	Rank 4	SAE (related to study product)

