10.5.8 Missing Data

The endpoints could be missing for subjects who withdraw from the trial or for other reasons. The reasons for withdrawal will be reported and compared qualitatively by arm. The effect that any missing data might have on results will be assessed via sensitivity analysis. If the pattern of missing data is different to that envisaged at the design stage, further sensitivity analyses will be provided that are tailored to the missing data pattern observed. The amount of missing data will be compared between randomized arms. The baseline characteristics of subjects with missing data will be compared to subjects without missing data.

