## 14.2 Microbiological Activity and Benefit to Risk Profile Data

**Table 19: Change from Baseline in *P. aeruginosa* Total Colony Counts in Quantitative Sputum Cultures by Treatment Group – ITT Population, Stage 2a and 2b**

[Implementation note: ‘Selected Dose’ will be replaced with the dose chosen by the interim analysis.]

Time Point	Treatment Group	Total Colony Counts						Change from Baseline						
		n	Mean	SD	Median	Q1, Q3 a	Min, Max	n	Mean	SD	Median	Q1, Q3 a	Min, Max	95% CI b
Baseline	Selected Dose (N=X)	x	xx.x	xx.x	xx.x	xx.x, xx.x	xx.x, xx.x	-	-	-	-	-	-	-
	Placebo (N=X)	x	xx.x	xx.x	xx.x	xx.x, xx.x	xx.x, xx.x	-	-	-	-	-	-	-
Day 1 Post-infusion	Selected Dose (N=X)	x	xx.x	xx.x	xx.x	xx.x, xx.x	xx.x, xx.x	x	xx.x	xx.x	xx.x	xx.x, xx.x	xx.x, xx.x	x.xx, x.xx
	Placebo (N=X)	x	xx.x	xx.x	xx.x	xx.x, xx.x	xx.x, xx.x	x	xx.x	xx.x	xx.x	xx.x, xx.x	xx.x, xx.x	x.xx, x.xx
Day 2	Selected Dose (N=X)	x	xx.x	xx.x	xx.x	xx.x, xx.x	xx.x, xx.x	x	xx.x	xx.x	xx.x	xx.x, xx.x	xx.x, xx.x	x.xx, x.xx
	Placebo (N=X)	x	xx.x	xx.x	xx.x	xx.x, xx.x	xx.x, xx.x	x	xx.x	xx.x	xx.x	xx.x, xx.x	xx.x, xx.x	x.xx, x.xx
Day 5	Selected Dose (N=X)	x	xx.x	xx.x	xx.x	xx.x, xx.x	xx.x, xx.x	x	xx.x	xx.x	xx.x	xx.x, xx.x	xx.x, xx.x	x.xx, x.xx
	Placebo (N=X)	x	xx.x	xx.x	xx.x	xx.x, xx.x	xx.x, xx.x	x	xx.x	xx.x	xx.x	xx.x, xx.x	xx.x, xx.x	x.xx, x.xx
Day 8	Selected Dose (N=X)	x	xx.x	xx.x	xx.x	xx.x, xx.x	xx.x, xx.x	x	xx.x	xx.x	xx.x	xx.x, xx.x	xx.x, xx.x	x.xx, x.xx
	Placebo (N=X)	x	xx.x	xx.x	xx.x	xx.x, xx.x	xx.x, xx.x	x	xx.x	xx.x	xx.x	xx.x, xx.x	xx.x, xx.x	x.xx, x.xx
Day 30	Selected Dose (N=X)	x	xx.x	xx.x	xx.x	xx.x, xx.x	xx.x, xx.x	x	xx.x	xx.x	xx.x	xx.x, xx.x	xx.x, xx.x	x.xx, x.xx
	Placebo (N=X)	x	xx.x	xx.x	xx.x	xx.x, xx.x	xx.x, xx.x	x	xx.x	xx.x	xx.x	xx.x, xx.x	xx.x, xx.x	x.xx, x.xx
Maximum	Selected Dose (N=X)	x	xx.x	xx.x	xx.x	xx.x, xx.x	xx.x, xx.x	x	xx.x	xx.x	xx.x	xx.x, xx.x	xx.x, xx.x	x.xx, x.xx
	Placebo (N=X)	x	xx.x	xx.x	xx.x	xx.x, xx.x	xx.x, xx.x	x	xx.x	xx.x	xx.x	xx.x, xx.x	xx.x, xx.x	x.xx, x.xx

Notes: N=Number of subjects in the ITT Population in Stage 2a and 2b.

n=Number of subjects in the ITT Population with non-missing colony counts at the time point of interest. For the change from baseline, n represents the number of subjects in the ITT population with non-missing values at baseline and at the time point being assessed.

SD=Standard Deviation

Baseline is defined as the last measurement taken prior to dosing on Study Day 1.

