Day 2	Selected IV Bacteriophage Dose (N=X)	xx	xx.x, xx.x
Day 5	Selected IV Bacteriophage Dose (N=X)	xx	xx.x, xx.x
Day 8	Selected IV Bacteriophage Dose (N=X)	xx	xx.x, xx.x
Day 30	Selected IV Bacteriophage Dose (N=X)	xx	xx.x, xx.x
Maximum	Selected IV Bacteriophage Dose (N=X)	xx	xx.x, xx.x

Notes: AUC will be calculated using the linear trapezoidal rule as the area under the curve between baseline and the given time point.

Undetectable results are treated as missing.

a The 95% CI for the difference in means is computed using Welch’s t-test.

**Table 13: Percentage of Subjects with Detectable, Undetectable, and Missing DOOR Data by Time Point, Stage, and Treatment Group – ITT Population**

[Implementation notes: ‘Selected IV Bacteriophage Dose’ will be replaced with the dose chosen by the interim analysis.

Time Point	Selected IV Bacteriophage Dose				Placebo				All Subjects			
	N	Detectable n (%)	Undetectable n (%)	Missing n (%)	N	Detectable n (%)	Undetectable n (%)	Missing n (%)	N	Detectable n (%)	Undetectable n (%)	Missing n (%)
Stage 2a												
Baseline	x	x	x	x	x	x	x	x	x	x	x	x
Day 1 Post-infusion	x	x	x	x	x	x	x	x	x	x	x	x
Day 2	x	x	x	x	x	x	x	x	x	x	x	x
Day 5	x	x	x	x	x	x	x	x	x	x	x	x
Day 8	x	x	x	x	x	x	x	x	x	x	x	x
Stage 2b												
...												

Notes: N=Number of subjects in the ITT population in each stage.

n=Number of subjects with missing data.

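### SAP 6.5 bars missing-data methods for every endpoint except DOOR, contrary to Protocol 10.5.8, so a subject with no Day 30 sputum is simply dropped from the co-primary log10 CFU change

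*SAP*

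**What the plan says.** Protocol 10.5.8 speaks of the endpoints without singling one out. It makes three commitments:

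- On robustness: "The effect that any missing data might have on results will be assessed via sensitivity analysis"
- On balance of loss: "The amount of missing data will be compared between randomized arms"
- On who is lost, it undertakes to set the baseline profile of those lacking data against that of those who have it.

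SAP 6.5 accepts that "some missing data is expected". It offers inverse probability weighting for DOOR, then closes the door on everything else: "No other endpoints will be analyzed using techniques for missing data".

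The microbiological co-primary endpoint in Protocol 3.3.1 runs later than DOOR: "Change from baseline to Day 30" (± 7 days) in log10 colony count. The notes to SAP Tables 19 and 20, repeated in the addendum, define who enters each change score: "n represents the number of subjects in the ITT population with non-missing values at baseline and at the time point being assessed". The between-arm difference comes from a Welch comparison at each visit (SAP Table 21; addendum Tables 5 and 6). SAP 8.1.2 computes AUC only for subjects with no missing count from baseline through Day 30.

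The dedicated missingness display is addendum Table 13, "Percentage of Subjects with Detectable, Undetectable, and Missing DOOR Data by Time Point, Stage, and Treatment Group", which replaces SAP Table 25. Its rows run from baseline to Day 8.

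**The concern.** The protocol makes a general promise and the SAP withdraws it for all but one endpoint. This is an explicit contrary rule rather than a detail left unstated. It falls on a co-primary endpoint measured about three weeks after DOOR closes, when withdrawal has had longest to act.

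Loss related to outcome is plausible from the protocol itself. Section 5.2.1 lists new clinical findings and a need for additional therapy among the reasons for withdrawal. Section 6.3.3 lets an early termination visit be done by telephone if the subject is too ill, and a telephone contact yields no sputum. SAP 8.1.3.1 says that an analysis of complete data alone can be biased when the excluded subjects differ systematically, but acts on this only for DOOR.

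At stake is whether the Day 30 estimate and its interval, on which SAP 8 relies for conclusions about treatment effect, can be read without an untested assumption about the subjects who gave no sample.

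**Working it through.** **1. Promise against plan, for the Day 30 log10 CFU change**

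| Protocol 10.5.8 | SAP and addendum |
|---|---|
| Sensitivity analysis for missing data | Excluded by SAP 6.5. The addendum treats undetectable counts only; its tipping-point analysis (Table 30) is for DOOR by Day 8 |
| Amount missing compared by arm | Tabulated to Day 8 only; Day 30 must be derived |
| Baseline comparison, with and without data | No shell in the SAP or addendum table lists |

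**2. What the addendum covers.** An undetectable count is replaced by the detection limit, 10^4 CFU/mL, in the primary analysis and set to missing in a sensitivity analysis. Both are carried to Day 30 (addendum Tables 1 to 6). At the interim, undetectable counts entered as null left 3 + 2 = 5 of 32 subjects (15.6%) without a change score. The substitution restores such subjects in the primary analysis. It does nothing for a subject with no sample.

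**3. What can be recovered at Day 30.** Addendum Tables 1 to 4 print N and n by arm at Day 30, so the number missing is N − n. The number undetectable is n in Table 3 minus n in Table 4. SAP Table 5 also reports Visit 7 completion by arm.

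**4. The plan's own figure.** The only precision statement is for DOOR: 51% to 89% at a DOOR probability of 70% with 20 per arm. The null Wilcoxon-Mann-Whitney standard error is √[(20+20+1)/(12×20×20)] = 0.0924. With t(38) = 2.024 this gives 0.70 ± 0.187, or 51.3% to 88.7%, which agrees on rounding. With z = 1.96 it gives 51.9% to 88.1%. It says nothing about Day 30 CFU, for which neither document gives an SD, a missing rate or a precision target.

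**5. Size of the bias.** All inputs here are assumptions: change scores normal with SD 1 to 2 log10; logit P(missing at Day 30) = b + ln(OR) × change, with positive change meaning worse and OR 2 to 4 per log10; difference taken as placebo minus phage. The mean among observed subjects was found by numerical integration.

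| Missing, placebo / phage | SD 1 | SD 2 |
|---|---|---|
| 10% / 10% | 0 | 0 |
| 10% / 20% | +0.06 to +0.10 | +0.20 to +0.26 |
| 20% / 10% | −0.06 to −0.10 | −0.20 to −0.26 |
| 5% / 25% | +0.13 to +0.20 | +0.41 to +0.54 |

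A positive figure overstates the benefit of phage. In the balanced row the difference is unbiased, but each arm's mean change still looks better than it is, by 0.07 to 0.12 log10 at SD 1. If one mechanism acts in both arms, with 20% missing on placebo and a true difference of 1 log10, the observed difference is 0.95 to 0.87 (SD 1) or 0.85 to 0.75 (SD 2), which is bias toward the null.

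**6. Scale.** The 95% half-width at 20 per arm is 2.024 × SD × √(2/20), which is 0.64 at SD 1 and 1.28 at SD 2. Bias as a share of it:

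- 10% / 20% missing: 0.063/0.64 = 10% up to 0.264/1.28 = 21%.
- One common mechanism: 0.053/0.64 = 8% up to 0.128/0.64 = 20%.
- 5% / 25% missing: 0.126/0.64 = 20% up to 0.536/1.28 = 42%.

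**7. What a repeated-measures estimate buys.** With missingness driven by worsening at Day 8 (400,000 simulated subjects per arm; SD 1; within-subject correlation 0.4 to 0.6; true difference −0.5, phage minus placebo; 13% to 19% missing on placebo and 6% to 8% on phage), the available-case difference was −0.43 to −0.48. An estimate using Days 2, 5 and 8 returned −0.50. If missingness follows only the Day 8 level under compound symmetry, the available-case bias is nil. The mechanism in step 5 depends on the Day 30 value itself, so it is not missing at random, and such a model would remove only the part that earlier visits predict.

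**The case against.** Several points on the other side stand, and they limit the finding.

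- **Visibility.** A reader might infer from the Day 8 cut-off that Day 30 missingness is hidden. It is not: step 3 shows that it can be derived by arm. Addendum Table 13 is titled for DOOR data, so its range follows its title. What is lacking is a direct display and comparison.
- **Undetectable counts.** A reader might infer from SAP 6.5 that nothing is done for this endpoint. The addendum came later and does treat undetectable counts through Day 30, which is the only loss the documents quantify. The gap is confined to absent samples.
- **Direction.** A reader might infer that the difference is shrunk toward zero, by 4% to 14% in the simulation of step 7. That follows from the mechanism assumed there. The documents support neither a direction nor those missing rates.
- **Conduct.** The protocol works against loss. Subjects given anti-pseudomonal antibiotics stay in (section 6), Day 30 may be virtual with a shipped sputum kit (6.4), and early termination visits aim to collect sputum (6.3.3). The colony-count tables, however, have no early termination row.
- **Remedy.** Protocol 10.5.8 names no method. An unstructured covariance over five post-dose visits has 5×6/2 = 15 parameters, to be estimated from 40 to 50 subjects on data floored at 10^4, and may not converge.
- **SAP 15.** It reports no change in conduct or planned analyses but does not mention the protocol, so it should not be read as denying this departure.

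The trial is also descriptive, with no hypothesis test on this endpoint. That lowers the stakes, but the estimate and interval then carry the whole conclusion. None of these points reconciles SAP 6.5 with Protocol 10.5.8.

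**Conclusion.** The inconsistency is established from the text alone. For the Day 30 log10 CFU change, the SAP expressly excludes the sensitivity analysis that the protocol promises; the baseline comparison has no shell; and the between-arm comparison of missingness stops at Day 8. The Day 30 difference is an available-case comparison, and AUC is a complete-case one.

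The numerical consequence is conditional. Outcome-related loss biases each arm's mean change. The difference may be overstated, understated or unaffected. Under moderate assumed imbalance the bias is a modest fraction of the interval's half-width; it approaches two fifths only under the most lopsided combination tried. These sizes rest on assumed SDs, missing rates and dependence on outcome. The point merits correction because the repair is cheap and the protocol already commits to it, not because a large bias has been shown.

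**What to change.** 1. Delete the sentence in SAP 6.5 that excludes the other endpoints.
2. Keep the Welch comparison. Beside it (SAP Table 21; addendum Tables 5 and 6), report as the protocol's sensitivity analysis a likelihood-based repeated-measures estimate of the Day 30 difference. Use all post-dose log10 changes, arm-by-visit means and an unstructured covariance, with a simpler structure named in advance in case of non-convergence. State that it assumes data missing at random.
3. Add a Day 30 row, by arm and stage, to addendum Table 13, and adjust its title so that it is not limited to DOOR.
4. Add a shell comparing baseline characteristics of subjects with and without a Day 30 count.

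The cost is SAP wording, one standard model and two small table additions. No new data are needed. The model does not test departures from missing at random. For a rough reading of those, moving one arm's missing subjects by 1 log10 shifts the difference by that arm's missing fraction: 0.05, 0.10 or 0.20 log10 at 5%, 10% or 20% missing.
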